10.62 All other AEs

Submit via appropriate MCCC Case Report Forms (i.e., paper or electronic, as applicable) the following AEs experienced by a patient and not specified in Section 10.6:

- 10.621 Grade 2 AEs deemed *possibly*, *probably*, *or definitely* related to the study treatment or procedure.
- 10.622 Grade 3 and 4 AEs regardless of attribution to the study treatment or procedure.

- 10.623 Grade 5 AEs (Deaths)
  - 10.6231 Any death within 30 days of the patient's last study treatment or procedure regardless of attribution to the study treatment or procedure.
    10.6232 Any death more than 30 days after the patient's last study
  - The first study treatment or procedure that is felt to be at least possibly treatment related must also be submitted as a Grade 5 AE, with a CTCAE type and attribution assigned.
- 10.7 Late Occurring Adverse Events

Refer to the instructions in the Forms Packet (or electronic data entry screens, as applicable) regarding the submission of late occurring AEs following completion of the Active Monitoring Phase (i.e., compliance with Test Schedule in Section 4.0).

# **11.0** Treatment Evaluation

# 11.1 Treatment evaluation using RECIST 1.1 guidelines

The first scan after treatment initiation will be performed at the completion of Cycle 4; scans will be then performed at the completion of every fourth cycle of treatment until disease progression is confirmed or withdrawn of consent. If a patient experiences PD yet continues protocol treatment, the next imaging should take place 2 cycles after the imaging showing PD. If that patient continues on protocol treatment, imaging should then take place every 4 cycles (See Section 4.0).

Disease progression for this protocol is defined as meeting the RECIST criteria for disease progression on two consecutive evaluations at least 6 weeks apart.

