#### 4.0 Study Schedules

#### 4.1 Test schedule for Melanoma

	≤14 days prior to	After	Cycle 1	Cycles	At completion of	End of
Tests and Procedures 	Registration	Reg	Day 1	2-3	each cycle (Cycle 3+)	Тх
window			$\pm 1 \text{ day}$	$\pm 3 \text{ days}$	$\pm 3 \text{ days}^2$	$\pm 7 \text{ days}$
Physical exam, weight, ECOG performance status	Х		Х	Х	Х	Х
Height	Х					
Serum pregnancy test	X 					
Hematology (WBC with differential, Hgb, PLT)	Х		X4		Х	Х
Chemistry profile (creatinine, AST, ALT, alkaline phosphatase, T bili, direct bilirubin, sodium, potassium, random glucose)	Х				Х	Х
Thyroid function cascade (TSH, reflex per Mayo standard if abnormal)	Х			Х	Х	Х
LDH	Х				Х	Х
Coagulation (INR)	Х			X 	$X^6$	
Adverse event assessment	Х				Х	Х
Radiologic evaluations (CT scan, PET/CT, or MRI)	X 				$X^8$	Х
Venous Access Assessment	X 					
Apheresis			Х			
Research blood for immune monitoring R (See Section 14.0) 		Х		X 	Х	Х
Research specimen submission: Tumor biopsies R (See Section 17.0)				X 	X 	

<sup>1 Cycle = 21 days; All tests and procedures are as clinically indicated, unless noted with an R to indicate funding by research. Hematology, chemistry profile, thyroid function cascade, coagulation tests, and imaging may be performed more frequently at physician discretion.

 Coagulation tests should be repeated at the completion of Cycles 1, 2, and 4. If treatment is delayed, coagulation tests should be repeated ≤48 hours prior to tumor biopsy.

 Coagulation tests should be repeated at the completion of Cycles 1, 2, and 4. If treatment is delayed, coagulation tests should be repeated ≤48 hours prior to tumor biopsy.

 Baseline radiology  $\leq 28$  days prior to registration

 Assessment of venous access must be done  $\geq$ 3 days prior to apheresis.

<sup>2 Window of 3 days applies to Cycles 2-5. After Cycle 5, window is  $\pm$ 7 days.

<sup>3 For persons of childbearing potential only. Must be done  $\leq$ 7 days prior to registration.

<sup>4 Repeat hematology tests on Cycle 1, Day 1 only if most recent tests were performed >7 days prior to Cycle 1, Day 1.

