<sup>8 Imaging is performed at the end of Cycle 4 and then at the end of every fourth cycle of treatment (end of Cycle 8, 12, 16, etc.). Exception: if a patient has PD yet continues protocol treatment, the next imaging should take place two cycles after the imaging showing PD. If that patient continues on protocol treatment, imaging should then take place every 4 cycles.

<sup>10 Blood draw for immune monitoring will be collected prior to the start of Cycles 1-5 and prior to the start of each post-imaging cycle thereafter (prior to Cycle 9, 13, 17, etc.)

<sup>11 In addition to the research blood collection on Day 1, research blood will be collected as per Section 14 on Cycle 2, Days 2-5. The collection on Cycle 2, Day 2 should take place 2-4 hours after completion of cryoablation and mDC therapy.

<sup>12 Tumor biopsies will be performed immediately prior to cryoablation on Cycle 2 Day 1 or 2 and Cycle 3 Day 1 or 2

<sup>13 Tumor biopsies will be performed at the end of Cycle 4 after radiologic evaluation

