#### 7.0 **Protocol Treatment**

Use actual weight or estimated dry weight if fluid retention.

Cycle length is 21 days with the exception of Cycle 1 which may be extended an additional 7 days to allow for dendritic cell production.

Dose-limiting toxicity (DLT) is defined as one of the following events occurring during the first two cycles of protocol therapy and attributed as possibly, probably, or definitely related to protocol therapy.

- Any Grade 3+ toxicity
- Grade 2 infusion reaction, acute or chronic kidney disease, or pneumonitis that does not resolve to Grade 0-1 within 3 weeks.

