# 8.2 Treatment schedule modifications for pembrolizumab.

Adverse events (both non-serious and serious) associated with pembrolizumab exposure may represent an immunologic etiology. These adverse events may occur shortly after the first dose or several months after the last dose of treatment. Pembrolizumab must be withheld for drug-related toxicities and severe or life-threatening AEs per Table 8.21 below. See Section 9.0 for supportive care guidelines, including use of corticosteroids.

CTCAE System/Organ/Class		a 1	
(SOC)	Adverse Event	Grade	Action
General disorders and administration site conditions	Infusion related reaction	2	Hold all protocol treatment until Grade 0-1 If AE does not resolve to Grade 0-1 within 3 weeks, then permanently discontinue all protocol treatment
		3-4	Permanently discontinue all protocol treatment
Respiratory, thoracic and mediastinal disorders	Pneumonitis	2	Hold all protocol treatment until Grade 0-1 If AE does not resolve to Grade 0-1 within 3 weeks, then permanently discontinue all protocol treatment
		3-4	Permanently discontinue all protocol treatment
Renal and urinary disorders.	Acute kidney injury or Chronic kidney disease	2	Hold all protocol treatment until Grade 0-1 If AE does not resolve to Grade 0-1 within 3 weeks, then permanently discontinue all protocol treatment
		3-4	Permanently discontinue all protocol treatment
	All Other Nonhematologic Events	3	Hold all protocol treatment until Grade 0-1 If AE does not resolve to Grade 0-1 within 3 weeks, then permanently discontinue all protocol treatment
		4	Permanently discontinue all protocol treatment

Table 8.21	Dose Modification Guidelines for Drug-Related Adverse Events
------------	--------------------------------------------------------------

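### On-treatment scans follow completed cycles with no calendar anchor, so a stretched cycle postpones the scan and makes the secondary PFS estimate partly dependent on dosing

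*Combined protocol and SAP*

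**What the plan says.** Section 11.1 sets the imaging rule: "The first scan after treatment initiation will be performed at the completion of Cycle 4", and afterwards "scans will be then performed at the completion of every fourth cycle of treatment until disease progression is confirmed". Footnote 8 to the test schedule in Section 4.1 repeats it: "Imaging is performed at the end of Cycle 4 and then at the end of every fourth cycle of treatment". The repeat scan after a first progression is also counted in cycles, two of them.

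Cycle length can vary. Section 7.0 states: "Cycle length is 21 days with the exception of Cycle 1 which may be extended an additional 7 days", to allow for dendritic cell production. For several toxicities Table 8.21 in Section 8.2 says "Hold all protocol treatment until Grade 0-1", with permanent discontinuation if the event has not resolved within 3 weeks. Section 8.1 gives one rule on numbering: an event in Cycle 2 that requires a hold means the Cycle 3 pembrolizumab is omitted and dosing resumes with Cycle 4.

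The test schedule anticipates delay, but only for laboratory tests: "If treatment is delayed, coagulation tests should be repeated ≤48 hours prior to tumor biopsy". It has no matching rule for scans. It does allow extra scans ("imaging may be performed more frequently at physician discretion") and sets a visit window ("Window of 3 days applies to Cycles 2-5", and 7 days either way after that).

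Median PFS is secondary goal 2.22. Section 16.34 estimates it by Kaplan-Meier from two consecutive evaluations showing progression about 6 weeks apart.

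**The concern.** Progression is known only when someone looks for it. If the date of looking depends on dosing, recorded PFS measures partly the disease and partly the dosing history. Two patients whose disease progresses on the same day can receive different PFS times because one had a manufacturing extension or a hold.

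This matters for goal 2.22 because a single-arm PFS median is read in absolute terms, with no control arm on the same scan schedule to absorb the shift. The clinical benefit rate in Section 16.33, defined by 6 completed cycles, has the same dependence.

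There is also a gap in the text. Outside the Cycle 2 rule, staff are not told whether a hold lengthens the current cycle or uses up a cycle number. Two people could date the same patient's scan 3 weeks apart and both be following the protocol.

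**Working it through.** **Inputs from the protocol.** Cycle length 21 days (7.0); Cycle 1 extension up to 7 days (7.0); maximum hold 3 weeks = 21 days (Table 8.21); first scan at the end of Cycle 4, then every fourth cycle (4.1 footnote 8, 11.1).

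**The plan's own figures.**
- Section 16.1 equates 4 cycles with about 84 days: 4 × 21 = 84. This reproduces, but only if no cycle stretches.
- Section 16.2 states 90% power for 33 patients, 12% against 30%, one-sided alpha 0.10. The exact binomial rule of at least 7 responses in 33 gives alpha 0.0930 and power 0.9056. This also reproduces, and scan timing does not enter the calculation.

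**Day of the first scan, if the delay stretches the cycle.**

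| Situation | Sum | Day |
|---|---|---|
| On schedule | 4 × 21 | 84 |
| Cycle 1 extension | 84 + 7 | 91 |
| One full hold | 84 + 21 | 105 |
| Both | 84 + 7 + 21 | 112 |

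**Effect on recorded PFS.** Assumptions not in the protocol: exponential progression times, true medians of 10 to 30 weeks, progression dated at the first scan that shows it, and a hold that stretches the cycle. Section 1.2 cites a 22-week median for pembrolizumab; it serves here only as one point in the range.

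Let λ = ln 2 / median and S(t) = exp(−λt). With scans every 12 weeks, mean recorded PFS is M = 12 / (1 − S(12)). One 3-week hold before the first scan puts scans at weeks 15, 27, 39 and so on, with mean 15 + S(15) × M.

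| True median (weeks) | S(12) | M | S(15) | Mean with hold | Change |
|---|---|---|---|---|---|
| 10 | 0.4353 | 21.25 | 0.3536 | 22.51 | +1.26 |
| 22 | 0.6852 | 38.12 | 0.6234 | 38.76 | +0.65 |
| 30 | 0.7579 | 49.56 | 0.7071 | 50.04 | +0.49 |

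**Direction.** Progression before week 12 is recorded at week 15 instead of week 12, 3 weeks later. Progression between weeks 12 and 15 is recorded at week 15 instead of week 24, 9 weeks earlier. The same pattern repeats at each later scan. The share recorded earlier is (1 − S(3)) × S(12) / (1 − S(12)): about 14% for a true median of 10 weeks and 21% for 30 weeks. The rest are recorded later.

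**Recorded median.** It can fall only on scan dates. If all patients were held, it would move from 12 to 15 weeks (true median 10), 24 to 27 (true median 22) or 36 to 39 (true median 30). A true median between 12 and 15 weeks would be the exception: the recorded median would fall from 24 to 15.

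**Whole cohort.** The frequency of holds is not in the protocol. If 25% of patients had one full hold (assumed), the cohort mean would rise by 0.25 × 0.49 = 0.12 to 0.25 × 1.26 = 0.32 weeks. The cohort's recorded median would still move from 24 to 27 for a true median of 22 weeks, and would stay at 36 for a true median of 30 weeks.

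**The case against.** A reader might infer that every toxicity hold postpones the scan, and that this flatters PFS in the patients who tolerate treatment worst. The protocol supports neither.

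- **Not every hold.** The only explicit rule, in Section 8.1, omits a dose and lets the numbering run on. Section 7.0 fixes the cycle at 21 days with one stated exception, the Cycle 1 extension. That a hold lengthens a cycle is the natural reading of holding all protocol treatment, but it is not stated. A Cycle 4 event would delay Cycle 5, so slippage of the first scan comes mainly from events in Cycles 1 or 3.
- **Not the worst-tolerating patients.** Table 8.21 permanently discontinues Grade 3-4 infusion reactions, pneumonitis and kidney events, other Grade 4 non-hematologic events, and the listed holds unresolved at 3 weeks. Those patients leave the cycle clock: they have an end-of-treatment scan and then event monitoring every 3 months until progression.
- **Day 112 is not a PFS effect.** It is the latest first-scan date with one hold, and 7 of its 28 extra days come from manufacturing, not toxicity.
- **Some protection exists.** Extra imaging is allowed, and symptomatic deterioration counts as progression (11.45). Both can shorten a delay, but neither sets a scan date.
- **The consequence is limited.** PFS is secondary and descriptive, with no test or power, and a single-arm trial has no between-arm comparison to bias.

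All of this narrows the point. It does not supply a calendar anchor, which the protocol lacks.

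**Conclusion.** The point holds in a limited form. Scan dates depend on completed cycles, cycles can stretch, and the numbering rule for most holds is missing. For patients whose hold resolves within 3 weeks, one full hold before the first scan raises mean recorded PFS by about 0.5 to 1.3 weeks, and the recorded median can rise by 3 weeks. These sizes rest on exponential progression, true medians of 10 to 30 weeks and a hold that stretches the cycle. The net direction of the mean is upward, but roughly one held patient in five to seven is recorded earlier. Section 16.34 does not say which of the two progression evaluations supplies the date, so the calculation uses the first.

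Patients who discontinue permanently are not affected through this route. The primary test, N = 33 and its power are unchanged. This is an inexpensive improvement to a secondary estimate, not a flaw in the main conclusion.

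**What to change.** 1. In Section 4.1 footnote 8 and Section 11.1, schedule scans at weeks 12, 24, 36 and so on from Cycle 1 Day 1, with the existing windows, regardless of holds or the Cycle 1 extension.
2. Keep the repeat scan after a first progression as a calendar interval of at least 6 weeks after the scan that showed it. This matches the two cycles now written (2 × 21 = 42 days).
3. In Section 16.1, express the response-confirmation interval in weeks to match the scan schedule. If it stays at 4 cycles or more, scans at weeks 12 and 24 with a hold between them could span fewer than 4 completed cycles, and a real response could fail the definition. The wording should also allow for the visit windows: scans 3 days late and then 7 days early would be 84 − 3 − 7 = 74 days apart.
4. Align Section 4.1 footnotes 10 and 13, which tie research blood and the biopsy to imaging and cycle ends.
5. State how holds outside the Cycle 2 rule count in cycle numbering. Which convention applies is for the sponsor to settle.

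The cost is wording, with no more scans per unit time. The downside is that, in a patient with a hold or the Cycle 1 extension, the week-12 scan may come before Cycle 4 is complete. With the full extension alone, Cycle 4 ends on day 91 and the scan is due on day 84. A scan may also not coincide with a treatment visit.

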# 11.2 Definitions of measurable and non-measurable disease

- 11.21 Measurable disease
  - 11.211 A non-nodal lesion is considered measurable if its longest diameter can be accurately measured as ≥1.0 cm with CT scan, CT component of a PET/CT, or MRI.
  - 11.212 A malignant lymph node is considered measurable if its short axis is  $\geq 1.5$  cm when assessed by CT scan (CT scan slice thickness recommended to be no greater than 5 mm).

**NOTE:** Tumor lesions in a previously irradiated area are not considered measurable disease.

11.22 Non-measurable disease

All other lesions (or sites of disease) are considered non-measurable disease, including pathological nodes (those with a short axis  $\geq 1.0$  to < 1.5 cm). Bone lesions, leptomeningeal disease, ascites, pleural/pericardial effusions, lymphangitis cutis/pulmonis, inflammatory breast disease, and abdominal masses (not followed by CT or MRI), are considered as non-measurable as well.

**NOTE:** 'Cystic lesions' thought to represent cystic metastases can be considered as measurable lesions, if they meet the definition of measurability described above. However, if non-cystic lesions are present in the same patient, these are preferred for selection as target lesions.

Lymph nodes that have a short axis <1.0 cm are considered non- pathological (i.e., normal) and should not be recorded or followed.

# 11.3 Guidelines for evaluation of measurable disease

- 11.31 Measurement methods:
  - All measurements should be recorded in metric notation (i.e., decimal fractions of centimeters) using a ruler or calipers.
  - The same method of assessment and the same technique must be used to characterize each identified and reported lesion at baseline and during follow-up. For patients having only lesions measuring at least 1 cm to less than 2 cm must use CT imaging for both pre- and post-treatment tumor assessments.

11.32 Acceptable modalities for measurable disease:

Conventional CT and MRI: This guideline has defined measurability of lesions on CT scan based on the assumption that CT slice thickness is 5 mm or less. If CT scans have slice thickness greater than 5 mm, the minimum size for a measurable lesion should be twice the slice thickness.

- As with CT, if an MRI is performed, the technical specifications of the scanning sequences used should be optimized for the evaluation of the type and site of disease. The lesions should be measured on the same pulse sequence. Ideally, the same type of scanner should be used and the image acquisition protocol should be followed as closely as possible to prior scans. Body scans should be performed with breath-hold scanning techniques, if possible.
- PET-CT: If the site can document that the CT performed as part of a PET-CT is of identical diagnostic quality to a diagnostic CT (with IV and oral contrast), then the CT portion of the PET-CT can be used for RECIST measurements and can be used interchangeably with conventional CT in accurately measuring cancer lesions over time.
- FDG-PET: FDG-PET scanning is allowed to complement CT scanning in assessment of progressive disease [PD] and particularly possible 'new' disease. A 'positive' FDG-PET scanned lesion is defined as one which is FDG avid with an update greater than twice that of the surrounding tissue on the attenuation corrected image; otherwise, an FDG-PET scanned lesion is considered 'negative.' New lesions on the basis of FDG-PET imaging can be identified according to the following algorithm:
  - a. Negative FDG-PET at baseline with a positive FDG-PET at follow-up is a sign of PD based on a new lesion.
  - b. No FDG-PET at baseline and a positive FDG-PET at follow-up:
    - i. If the positive FDG-PET at follow-up corresponds to a new site of disease confirmed by CT, this is PD.
    - ii. If the positive FDG-PET at follow-up is not confirmed as a new site of disease on CT at the same evaluation, additional follow-up CT scans (i.e., additional follow-up scans at least 4 weeks later) are needed to determine if there is truly progression occurring at that site. In this situation, the date of PD will be the date of the initial abnormal PDG-PET scan.
    - iii If the positive FDG-PET at follow-up corresponds to a pre-existing site of disease on CT that is not progressing on the basis of the anatomic images, it is not classified as PD.
- The cytological confirmation of the neoplastic origin of any effusion that appears or worsens during treatment when the measurable tumor has met criteria for response or stable disease is mandatory to differentiate between response or stable disease (an effusion may be a side effect of the treatment) and progressive disease.

• Cytologic and histologic techniques can be used to differentiate between PR and CR in rare cases (e.g., residual lesions in tumor types such as germ cell tumors, where known residual benign tumors can remain.)

# 11.4 Measurement of effect

- 11.41 Target lesions & target lymph nodes
  - Measurable lesions (as defined in Section 11.21) up to a maximum of 5 lesions, representative of all involved organs, should be identified as "Target Lesions" and recorded and measured at baseline. These lesions can be non-nodal or nodal (as defined in 11.21), where no more than 2 lesions are from the same organ and no more than 2 malignant nodal lesions are selected.

**Note:** If fewer than 5 target lesions and target lymph nodes are identified (as there often will be), there is no reason to perform additional studies beyond those specified in the protocol to discover new lesions.

- Target lesions and target lymph nodes should be selected on the basis of their size, be representative of all involved sites of disease, but in addition should be those that lend themselves to reproducible repeated measurements. It may be the case that, on occasion, the largest lesion (or malignant lymph node) does not lend itself to reproducible measurements in which circumstance the next largest lesion (or malignant lymph node) which can be measured reproducibly should be selected.
- Baseline Sum of Dimensions (BSD): A sum of the longest diameter for all target lesions plus the sum of the short axis of all the target lymph nodes will be calculated and reported as the baseline sum of dimensions (BSD). The BSD will be used as reference to further characterize any objective tumor response in the measurable dimension of the disease.
- Post-Baseline Sum of the Dimensions (PBSD): A sum of the longest diameter for all target lesions plus the sum of the short axis of all the target lymph nodes will be calculated and reported as the post-baseline sum of dimensions (PBSD). If the radiologist is able to provide an actual measure for the target lesion (or target lymph node), that should be recorded, even if it is below 0.5 cm. If the target lesion (or target lymph node) is believed to be present and is faintly seen but too small to measure, a default value of 0.5 cm should be assigned. If it is the opinion of the radiologist that the target lesion or target lymph node has likely disappeared, the measurement should be recorded as 0 cm.
- The minimum sum of the dimensions (MSD) is the minimum of the BSD and the PBSD.
- 11.42 Non-target lesions & non-target lymph nodes

Non-measurable sites of disease (Section 11.22) are classified as non-target lesions or non-target lymph nodes and should also be recorded at base line. These lesions and lymph nodes should be followed in accord with 11.433.

- 11.43 Response criteria
  - 11.431 All target lesions and target lymph nodes followed by CT/MRI/PET-CT must be measured on re-evaluation at evaluation times specified in Section 11.1. Specifically, a change in objective status to either a PR or

CR cannot be done without re-measuring target lesions and target lymph nodes.

**Note:** Non-target lesions and non-target lymph nodes should be evaluated at each assessment, especially in the case of first response or confirmation of response. In selected circumstances, certain non-target organs may be evaluated less frequently. For example, bone scans may need to be repeated only when complete response is identified in target disease or when progression in bone is suspected.

11.432 Evaluation of target lesions

	Complete Response (CR):	

All of the following must be true:

a. Disappearance of all target lesions.

b. Each target lymph node must have reduction in short axis to <1.0 cm.

				
	Partial Response (PR):	At least a 30% decrease in PBSD (sum of the longest diameter for all target lesions plus the sum of the short axis of all the target lymph nodes at current evaluation) taking as reference the BSD ( see Section 11.41).				
	Progression (PD):	At least one of the following must be true:				
		a. At least one new malignant lesion, which also includes any lymph node that was normal at baseline (<1.0 cm short axis) and increased to $\geq$ 1.0 cm short axis during follow-up.				
		
 
b. At least a 20% increase in PBSD (sum of the longest diameter for all target lesions plus the sum of the short axis of all the target lymph nodes at current evaluation) taking as reference the MSD (Section 11.41). In addition, the PBSD must also demonstrate an absolute increase of at least 0.5 cm from the MSD.
 
				
		c. See Section 11.32 for details in regards to the requirements for PD via FDG-PET imaging.				
	Stable Disease (SD):	Neither sufficient shrinkage to qualify for PR, nor sufficient increase to qualify for PD taking as reference the MSD.				
11.433	Evaluation of Non-Target Le	sions & Non-target Lymph Nodes				
	Complete Response (CR):	All of the following must be true:				
		a. Disappearance of all non-target lesions.				

	b.	Each non-target lymph node must have a reduction in short axis to <1.0 cm.
Non-CR/Non-PD:		rsistence of one or more non-target sions or non-target lymph nodes.
Progression (PD):	At tru	least one of the following must be le:
	a.	At least one new malignant lesion, which also includes any lymph node that was normal at baseline (<1.0 cm short axis) and increased to $\geq$ 1.0 cm short axis during follow- up.
	b.	Unequivocal progression of existing non-target lesions and non-target lymph nodes. (NOTE: Unequivocal progression should not normally trump target lesion and target lymph node status. It must be representative of overall disease status change.)
	c.	See Section 11.32 for details in regards to the requirements for PD via FDG-PET imaging.

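### Lesions scheduled for cryoablation may serve as RECIST targets, so local change in a frozen lesion can count toward PR or PD; the plan should record these lesions separately and add a response analysis on non-ablated targets

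*Combined protocol and SAP*

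**What the plan says.** All references are to the combined protocol and SAP.

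- **Target selection (11.41).** "Measurable lesions (as defined in Section 11.21) up to a maximum of 5 lesions, representative of all involved organs, should be identified as" target lesions. The basis for choice follows: "Target lesions and target lymph nodes should be selected on the basis of their size, be representative of all involved sites of disease". The section also asks for lesions that can be measured reproducibly. It does not mention ablation.
- **Local treatment (11.21, NOTE).** "Tumor lesions in a previously irradiated area are" not considered measurable. There is no matching rule for lesions that the trial itself will freeze.
- **Ablation (7.5).** Two distinct metastases are frozen, one in Cycle 2 and one in Cycle 3. The iceball must reach at least 75% of the tumor diameter and may cover the whole tumor with a margin of normal tissue.
- **Timing (11.1).** "The first scan after treatment initiation will be performed at the completion of Cycle 4".
- **Response and progression (11.432).** PR is "At least a 30% decrease in PBSD" relative to the baseline sum (BSD). PD on target lesions is "At least a 20% increase in PBSD" relative to the minimum sum (MSD), with an absolute rise of at least 0.5 cm.
- **Very small or vanished targets (11.41).** For a target seen but too small to measure, "a default value of 0.5 cm should be assigned". For one that in the radiologist's opinion "has likely disappeared, the measurement should be recorded as 0 cm".
- **Non-target disease (11.42).** Only non-measurable sites are given non-target status.
- **Entry (3.15).** At least three lesions, with at least one measurable and at least two suitable for ablation.
- **Primary endpoint (16.1).** RECIST PR or CR on two consecutive evaluations at least 4 cycles apart, among all who started treatment at the continuation level.

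**The concern.** The trial delivers a destructive local treatment to two lesions per patient and then reads response from a sum that may include them. Section 1.5 describes freezing as killing cells directly, so a change in the size of a frozen lesion is expected whether or not an immune response follows. The direction is open: the lesion may shrink, or the ablation zone may measure larger than the tumor it replaced.

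Section 1.6 asks whether the combination generates anti-tumor immunity and clinical regression. A PR that comes only from the frozen lesions does not show regression anywhere else, and a PD that comes only from an enlarged ablation zone does not show treatment failure. Two readers who follow 11.41 correctly could choose different targets in the same patient and classify that patient differently. The reported rate would not reveal which kind of response was counted.

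**Working it through.** **1. The plan's own design figure (16.2).** Inputs: n = 33, null 12%, alternative 30%, one-sided 0.10, exact binomial. P(X ≥ 6 | 33, 0.12) = 0.198 and P(X ≥ 7 | 33, 0.12) = 0.093, so the test rejects at 7 or more responders. P(X ≥ 7 | 33, 0.30) = 0.906. The stated 90% power is reproduced.

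**2. Timing.** With 21-day cycles, the start of Cycle 2 is 3 × 21 = 63 days (9 weeks) before the end of Cycle 4, and the start of Cycle 3 is 2 × 21 = 42 days (6 weeks) before it. Both ablations fall between the baseline sum and the first response scan.

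**3. Change needed in the ablated targets alone.** Assume T equal targets, k of them ablated, the others unchanged, no new lesion and no non-target progression. At the first scan the MSD before that scan is the BSD. Then:

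- PR needs each ablated target to shrink by 0.30 × T/k.
- PD needs each to grow by 0.20 × T/k, and the sum to rise by at least 0.5 cm.

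| Targets (T) | Ablated (k) | PR: each smaller by | PD: each larger by (20% rule) |
|---|---|---|---|
| 3 | 2 | 45% | 30% |
| 4 | 2 | 60% | 40% |
| 5 | 2 | 75% | 50% |
| 2 | 2 | 30% | 20% |
| 1 | 1 | 30% | 20% |
| 2 | 1 | 60% | 40% |
| 3 | 1 | 90% | 60% |

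With one ablated among 4 or 5 targets the PR formula gives 120% or 150%, so that lesion alone cannot produce PR.

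**4. The 0.5 cm rule.** For non-nodal targets of 1.0 cm, a 20% rise in the sum is 0.2 × T cm. This falls short of 0.5 cm when T is 1 or 2, so the absolute rule then sets the PD threshold: 0.5/1.0 = 50% for 1 of 1, 0.25/1.0 = 25% for 2 of 2, and 0.5/1.0 = 50% for 1 of 2. With T = 3 the rise is 0.6 cm and the rule no longer binds.

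**5. Recording rules in 11.41.** Ablated targets recorded as 0 cm lower the sum by k/T. For k = 2 that is 67%, 50% or 40% with 3, 4 or 5 targets, which is PR each time. For k = 1 it is 33%, 25% or 20%, which is PR only with 3. If two 1.0 cm targets take the 0.5 cm default, the sum falls by 0.5 × 2/T = 33%, 25% or 20%, which is PR only with 3.

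**6. What a shift in the counted rate would do (assumption only).** The documents give no measurements of ablated lesions, so these inputs are illustrative.

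- If local change moved the counted rate from 12% to 15%, the chance of rejecting would go from 0.093 to 0.217.
- If it cost one responder per 33 at 30% (0.30 − 1/33 = 27.0%), the chance would go from 0.906 to 0.826.

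**The case against.** **Goal 2.1 is the response rate of the whole regimen.** Cryoablation and intratumoral cells are part of that regimen, so change in treated lesions is part of what the goal asks. This stands. A reader might infer that the primary endpoint must move to non-ablated lesions. The documents do not require that, and the move would change what the 12% and 30% in 16.2 refer to.

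**Section 3.15 points to a separate measurable lesion.** Its count of one measurable plus two ablatable lesions, three in all, reads that way. It also does not require the ablatable lesions to be measurable; if they are not, they cannot be targets. Both points limit how often the problem can arise and make the cases where every target is ablated the least likely. But 3.15 governs entry and sets minimum counts. It does not say which lesions become targets.

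**Other rules protect the endpoint.** Response must hold about 84 days later (16.1), PD must be seen twice at least 6 weeks apart (11.1), and new lesions or unequivocal non-target progression override the sum (11.44). Ablation alone also cannot give an overall CR while other disease persists. These rules test persistence and detect progression elsewhere. A frozen lesion that stays small while the rest is stable still yields a confirmed PR.

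**Type I error.** A reader might infer that the 0.10 level is breached. The null in 16.2 concerns the response rate as 16.1 defines it. If that rate is above 12% the null is false, and rejecting it is not a type I error. The 0.217 is error inflation only if 12% means a rate in non-ablated lesions, and 16.2 does not say so.

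**Conclusion.** The gap is real. Following the plan exactly can produce a confirmed PR, or a PD, from local change in frozen lesions with no change elsewhere. It applies only when an ablated lesion is measurable and is chosen as a target.

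The size can be stated only as thresholds, under equal targets and no change elsewhere. With two ablated among three targets, a 45% reduction in each is enough for PR and a 30% increase in each is enough for target-lesion PD. A reader might infer that the reported response rate will be inflated. The documents do not support that: they give neither the frequency nor the net direction, and enlargement would act the other way. The sample size of 33 is correct for its stated inputs. This is an inexpensive improvement to the endpoint definition and reporting.

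**What to change.** **11.41.** Record at baseline which lesions are planned for ablation, and measure and report them separately. Where other measurable lesions exist, select at least one of them as a target. State how a lesion named for ablation but never frozen is handled.

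**16.1.** Keep the whole-regimen response rate of goal 2.1. Add a prespecified analysis of response based on non-ablated target lesions only, reported beside the primary result. State how patients with no measurable non-ablated lesion are counted in it, since the primary denominator is everyone who started treatment at the continuation level.

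**11.42 to 11.44.** State how ablated lesions count for CR and PD. At present a measurable lesion left out of the target set has no defined category.

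Whether the non-ablated rate should instead be primary is the sponsor's choice. If so, the 12% and 30% would need to be restated for that endpoint.

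**Cost.** Protocol wording, a little more measurement bookkeeping and one more analysis. With the primary endpoint kept as it is, the sample size calculation is unaffected. The added rate may be lower than the primary rate and may rest on a single lesion in some patients.
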